10.3.1.2 Potential Cases of Drug-induced Liver Injury

Refer to [Section 10.4, Appendix 4: Liver Safety Monitoring and Assessment] for detailed instructions on drug induced liver injury. Abnormal values in AST and/or ALT concurrent or with abnormal elevations in TBL that meet the criteria outlined in [Section 10.4, Appendix 4: Liver Safety Monitoring and Assessment], in the absence of other causes of liver injury, are considered potential cases of drug-induced liver injury (potential Hy's Law cases) and are always to be considered important medical events and reported per [Section 10.3.6 Reporting Procedures for Serious Adverse Events].

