10.4 Appendix 4: Liver Safety Monitoring and Assessment

The purpose of this appendix is to provide guidance for the monitoring of drug-induced liver injury during the course of the study. It should be noted that this section does not specify the end-of-study analyses of liver enzymes. The end-of-study liver enzymes analyses will be described in the SAP. Any participant enrolled in the study with active drug therapy and reveals an increase of serum aminotransferases (AT) to $> 3 \times ULN$ or TBL $> 2 \times ULN$ should undergo detailed testing for liver enzymes (including at least gamma-glutamyltransferase [GGT], ALT, AST, alkaline phosphatase [ALP], TBL and glutamate dehydrogenase). Participants whose baseline ALT or AST values were $> 3 \times ULN$ (with elevated creatine kinase [CK]) and who have a clinically significant rise as assessed by the investigator should also undergo detailed testing for liver enzymes. Testing should be repeated within 72 hours of notification of the test results. For studies for which a central laboratory is used, alerts will be generated by the central laboratory regarding moderate and severe liver abnormality to inform the investigator and study team. Participants should be asked if they have any symptoms suggestive of hepatobiliary dysfunction.

In addition, free triiodothyronine (FT3), free thyroxine (FT4) and thyroid stimulating hormone (TSH) should be measured to monitor the thyroid function in case of hepatobiliary dysfunction. If FT3, FT4 or TSH show any abnormalities and/or clinically significant symptoms, the investigator should determine if further follow up of liver chemistry tests and/or thyroid function tests are required.

For cases with concurrent CK elevation, participants should undergo detailed testing for liver enzymes (including at least GGT, ALT, AST, ALP, TBL and glutamate dehydrogenase). Once the investigator can confirm absence of hepatobiliary injury based on the detailed liver enzyme testing, the investigator will determine if further follow up of liver chemistry tests are required. If concurrent hepatobiliary injury cannot be ruled out, the guidance should be followed as described in Follow-up Procedures in this appendix.

Definition of Liver Abnormalities

Confirmed abnormalities will be characterized as moderate and severe where ULN is as shown below.

Table 9	Moderate and Severe Liver Abnormalities
---------	---

	ALT or AST		TBL
Moderate	$> 3 \times ULN$	or	$> 2 \times ULN$

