Severe	$> 3 \times ULN$	and†	$> 2 \times ULN$

ALT: alanine aminotransferase; AST: aspartate aminotransferase; TBL: total bilirubin; ULN: upper limit of normal

†Samples taken simultaneously or within maximum 24 hours.

In addition, the participant should be considered to have severe hepatic abnormalities for any of the following:

- ALT or AST $> 8 \times ULN$
- ALT or AST > $5 \times$ ULN for more than 2 weeks

- ALT or AST > 3 × ULN and† international normalized ratio (INR) > 1.5 (If INR testing is applicable/evaluated)
- ALT or $AST > 3 \times ULN$ with the appearance of fatigue, nausea, vomiting, right upper quadrant pain or tenderness, fever, rash and/or eosinophilia (> 5%)

†Samples taken simultaneously or within a maximum of 24 hours.

The investigator may determine that abnormal liver chemistry results, other than as described above, may qualify as moderate or severe abnormalities and require additional monitoring and follow-up.

Follow-up Procedures

Confirmed moderate and severe abnormalities in hepatic functions should be thoroughly characterized by obtaining appropriate expert consultations, detailed pertinent history, physical examination and clinical laboratory tests. The study site personnel are to complete the liver abnormality case report form (LA-CRF). Participants with confirmed abnormal liver function testing should be followed as described below.

Confirmed moderately abnormal liver function tests should be repeated 2 to 3 times weekly, and then weekly or less if abnormalities stabilize or the IP has been discontinued and the participant is asymptomatic.

Severe hepatic liver function abnormalities as defined above, in the absence of another etiology, may be considered an important medical event and may be reported as a SAE. The sponsor should be contacted and informed of all participants for whom severe hepatic liver function abnormalities possibly attributable to IP are observed.

To further assess abnormal hepatic laboratory findings, the investigator is expected to:

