- Evidence that a drug can cause hepatocellular-type injury, generally shown by an increase in AT elevations > 3 × ULN ("2 × ULN elevations are too common in treated and untreated participants to be discriminating").
- Cases of increased TBL (at least 2 × ULN) with concurrent AT elevations at least 3 × ULN and no evidence of intra- or extra-hepatic bilirubin obstruction (elevated ALP) or Gilbert's syndrome [Temple, 2006].

FDA Guidance for Industry titled, "Drug-induced Liver Injury: Premarketing Clinical Evaluation" issued by the FDA on July 2009:

- The drug causes hepatocellular injury, generally shown by a higher incidence of 3-fold or greater elevations > ULN of ALT or AST than the (nonhepatotoxic) control drug or placebo.
- Among participants showing such AT elevations, often with ATs much greater than 3 × ULN, one or more also show elevation of serum TBL to > 2 × ULN, without initial findings of cholestasis (elevated serum ALP).
- 3. No other reason can be found to explain the combination of increased AT and TBL, such as viral hepatitis A, B or C; preexisting or acute liver disease; or another drug capable of causing the observed injury.

Type of Prohibited Medication	Name of Medication
PPAR ligands	clinofibrate, clofibrate, fenofibrate, gemfibrozil, fibrates, thiazolidinediones
P-gp substrates	dabigatran, digoxin, fexofenadine
BCRP substrates	rosuvastatin, sulfasalazine
OATP1B1 and OATP1B3 substrates	asunaprevir, atorvastatin, bosentan, danoprevir, docetaxel, fexofenadine, nateglinide, paclitaxel, repaglinide, rosuvastatin, simvastatin
OAT3 substrates	cefaclor, ceftizoxime, famotidine, furosemide, methotrexate, oseltamivir carboxylate, penicillin G
Strong and Moderate Inhibitors of CYP3A	boceprevir, cobicistat, danoprevir/ritonavir, elvitegravir/ritonavir, grapefruit juice, indinavir/ritonavir, itraconazole, ketoconazole, lopinavir/ritonavir, paritaprevir/ritonavir/(ombitasvir and/or dasabuvir), posaconazole, ritonavir, saquinavir/ritonavir, telaprevir, tipranavir/ritonavir, telithromycin, troleandomycin, voriconazole, clarithromycin, idelalisib, nefazodone, nelfinavir, aprepitant, ciprofloxacin, conivaptan, crizotinib, cyclosporine, diltiazem, dronedarone, erythromycin, fluconazole, fluvoxamine, imatinib, tofisopam, verapamil
BCRP inhibitors	curcumin, cyclosporine A, eltrombopag

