6.5.2.1 Liver Safety Assessment

The liver safety assessments will be summarized by the categories below based on the measurements from ALP, ALT, total bilirubin, AST and their combination. These parameters will be based on measurements from a local laboratory. If the baseline value is above ULN then use the baseline value instead of ULN.

- ALT > ULN, > 2xULN, > 3xULN, > 5xULN, > 10xULN, > 20xULN
- AST > ULN, > 2xULN, > 3xULN, > 5xULN, > 10xULN, > 20xULN
- ALT or AST > ULN, > 2xULN, > 3xULN, > 5xULN, > 10xULN, > 20xULN
- ALP > 1.5xULN, 2xULN, 2.5xULN
- Total Bilirubin > 2xULN
- (ALT or AST > 3xULN) and Total Bilirubin > 2xULN
- (ALT or AST > 3xULN) and ALP < 2xULN and Total Bilirubin > 2xULN

The last 2 criteria where 2 or more parameters are evaluated will be with the measurements on the same day or up to 1 day apart.

The denominator for each criterion will be the number of participants who have at least one value after the day of first dose taken to 28 days after the last dose of IP for the 52 weeks or moving to the OLE, whichever comes first. The number and percentage of participants meeting the criteria by 28 days after the last dose of IP for the 52 weeks or moving to the OLE will be summarized by analysis group.

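### Liver rows labelled xULN use the participant's own baseline when it is above ULN, so a participant with the protocol's combined ALT/AST and bilirubin values can be missing from the SAP's combined rows

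*SAP*

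**What the plan says.** Section 6.5.2.1 (Liver Safety Assessment) is in substance the same in the 52-week and 76-week SAPs. It states the substitution, "If the baseline value is above ULN then use the baseline value instead of ULN", and then lists the rows: ALT, AST, and ALT or AST from above ULN to above 20xULN; ALP above 1.5, 2 and 2.5xULN; TBL above 2xULN; and two combined rows, ("ALT or AST > 3xULN) and Total Bilirubin > 2xULN" and ("ALT or AST > 3xULN) and ALP < 2xULN and Total Bilirubin > 2xULN". The measurements in a combined row must fall on the same day or at most one day apart.

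Protocol Appendix 4 (Section 10.4) works from ULN itself: "Confirmed abnormalities will be characterized as moderate and severe where ULN is as shown below". Table 9 then makes ALT or AST above 3xULN together with TBL above 2xULN severe, on samples no more than 24 hours apart. The Hy's Law text in the same appendix is also in ULN multiples: "Cases of increased TBL (at least 2 × ULN) with concurrent AT elevations at least 3 × ULN". The appendix has one baseline provision, for participants who start with ALT or AST above 3xULN and raised CK. It adds detailed testing after a clinically significant rise and does not change the definitions. The appendix leaves the end-of-study liver enzyme analysis to the SAP.

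**The concern.** The row labels say xULN, but for anyone whose baseline was above ULN the computation uses multiples of baseline. The first combined row has the same two multiples as Table 9's severe line and nearly the same time window. A reader will naturally take it as the number of participants who reached those values.

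Raised baselines are foreseen. Exclusion 6 (protocol Section 5.2) bars raised transaminases only when CK is not raised, and lets slightly raised TBL, ALT or AST in after discussion. Appendix 4 provides for baselines above 3xULN. Safety is a primary objective, and a combined row reading zero would be taken as reassurance on liver injury when a participant might have reached the protocol's values.

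**Working it through.** The plan gives no figure to reproduce; the check applies both rules to the same participant.

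**Inputs.** Protocol severe combination (Table 9): ALT or AST > 3xULN and TBL > 2xULN. SAP combined row (6.5.2.1, both SAPs): the same multiples, with baseline replacing ULN if baseline is above ULN.

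**Formula.** Write every value as a multiple of ULN, with baseline b and reference R(b) = max(1, b).

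- Protocol: ALT > 3 and TBL > 2.
- SAP: ALT > 3 × R(baseline ALT) and TBL > 2 × R(baseline TBL).

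**Cases.** Baseline and on-treatment values are assumptions chosen for illustration. AST is taken not to qualify, and the values are taken as confirmed. All seven meet the protocol's combined values.

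| Baseline ALT / TBL | On-treatment ALT / TBL | SAP row needs ALT / TBL | In SAP combined row? |
|---|---|---|---|
| 0.8 / 0.8 | 3.5 / 2.5 | > 3.0 / > 2.0 | yes |
| 1.2 / 0.8 | 3.5 / 2.5 | > 3.6 / > 2.0 | no |
| 1.5 / 0.8 | 4.0 / 2.5 | > 4.5 / > 2.0 | no |
| 2.0 / 0.8 | 5.0 / 2.5 | > 6.0 / > 2.0 | no |
| 3.0 / 0.8 | 8.5 / 2.5 | > 9.0 / > 2.0 | no |
| 3.5 / 0.8 | 9.0 / 3.0 | > 10.5 / > 2.0 | no |
| 0.8 / 1.2 | 4.0 / 2.3 | > 3.0 / > 2.4 | no |

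The six participants with one raised baseline are missed under the SAP rule and counted under fixed ULN. The one with normal baselines is counted either way. The second combined row only adds an ALP condition, so whoever fails the first row on ALT or TBL fails the second too.

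**ALP.** Here the shift goes the other way. With baseline ALP 1.5xULN, the ALP < 2xULN condition becomes ALP < 2 × 1.5 = 3.0xULN. An on-treatment ALP of 2.5xULN fails under fixed ULN and passes under the SAP rule.

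**Other planned counts.** Neither SAP tabulates these rows against unmodified ULN. Section 6.5.2 gives summaries by visit and, in the 76-week SAP, a low/normal/high classification; neither pairs ALT or AST with TBL in one participant. The same section counts amylase, lipase and troponin above ULN and 2xULN with no substitution stated, so the label changes meaning between adjacent subsections.

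**The case against.** The case for the SAP's rule is a reasonable one. Muscle disease can raise transaminases, and the protocol itself refers CK to the higher of ULN and baseline. The substitution is stated openly above the rows. Appendix 4 says it does not specify the end-of-study analysis, and neither SAP names Table 9 or Hy's Law for these rows, so no protocol rule is broken. The SAP rows also leave out Table 9's companion criteria (8xULN, duration, INR, symptoms), so they were not built to reproduce the whole severe category. All of that stands. It justifies showing baseline multiples, but not labelling them xULN, nor having no fixed-ULN count of the combination.

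Cases are also not lost from the study. Laboratory data are listed (protocol Section 9.4.3.2), maxima by visit use unmodified values, and SAE reporting and the liver abnormality case report form remain. A participant whose AST baseline was normal can still enter through the ALT-or-AST wording. This limits the point to the summary count.

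A reader might infer that the table hides cases that must always be reported. The documents do not support that. Protocol Section 10.3.1.2 says of potential Hy's Law cases that they "are always to be considered important medical events and reported per" the SAE procedures, but only where other causes of liver injury are absent. For severe abnormalities Appendix 4 says only that they may be reported as an SAE.

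**Conclusion.** The point holds for the summary tables. In 6.5.2.1 of both SAPs the xULN label and the computation disagree for anyone with a baseline above ULN, and a participant who reaches the protocol's combined values can be absent from both combined rows. The effective limit is the stated multiple times the baseline: 4.5xULN instead of 3xULN at baseline ALT 1.5xULN, and 2.4xULN instead of 2xULN at baseline TBL 1.2xULN.

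This rests on reading the substitution as covering every row, which its placement and the lack of any exemption support, and on some participants having a raised baseline. The omission is possible, not shown.

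Two further inferences should be resisted. One is that every count falls: that is true of the > conditions, but the ALP < 2xULN condition is loosened. The other is a number of participants affected. No baseline distribution is given, and the planned 66 is not a safe denominator, because SAP Section 6.7.1 reports an interim on the first 33 and a recommendation to stop for futility. Exclusion 6 is also quoted from Version 9.0, whereas the SAPs say that all participants enrolled under Version 7.0 or earlier.

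**What to change.** In 6.5.2.1 of both SAPs, compute the rows labelled xULN against fixed ULN for all participants; the two combined rows matter most. Keep the baseline-multiple version as a second block, labelled as multiples of baseline and restricted to participants whose baseline was above ULN.

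The cost is a wording change in two documents and one extra block in an existing table, from data already planned. If the SAPs can no longer be revised, the fixed-ULN rows can be added and recorded in the clinical study report, as the SAP introductions provide for changes. The downside is that chronically raised values, likely from muscle, will appear in the fixed-ULN rows; the second block shows which ones they are.

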6.5.3 Vital Signs

Vital signs (systolic blood pressure, diastolic blood pressure, and pulse rate) will be summarized using mean, standard deviation, minimum, maximum and median by analysis group and visit. Additionally, a within-participant change will be calculated per visit as the

post-baseline measurement minus the baseline measurement and summarized by analysis group and visit.

6.5.4 Electrocardiograms

6.5.4.1 Routine 12-lead Electrocardiograms

The number and percent of participants with normal, not clinically significant abnormal, and clinically significant abnormal results as assessed by site principal investigator for the 12 lead ECG will be tabulated by analysis group and time point. Continuous 12-lead Electrocardiogram

For all analyses, replicates at each visit will be averaged for each continuous ECG parameter.

ECG parameters [Heart Rate (bpm), PR Interval (ms), QRS Interval (ms) and QTcF (ms)] read by the central laboratory will be summarized using mean, standard deviation, minimum, maximum and median for each analysis group at each visit, including changes from baseline.

The QTcF interval will be summarized using frequency tables for each visit for values of clinical importance using the range criteria below.

	QTcF Interval Criteria Value (msec)
Normal	\leq 450
Borderline	> 450
Prolonged	> 480
Clinically significant	> 500

QTcF: QT interval using Fridericia's correction.

The QTcF interval will also be summarized by the frequencies of participants with an increase from baseline of clinical importance using the criteria identified below. These summaries will be provided for each visit.

Variable	Change from Baseline
QTcF Interval (msec)	\leq 30
	> 30
	> 60

QTcF: QT interval using Fridericia's correction.

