- 12. Participant has clinically significant and unstable respiratory disease and/or cardiac disease (medical history or current clinical findings) in the opinion of the investigator, or prior interventional cardiac procedure (e.g., cardiac catheterization, angioplasty/ percutaneous coronary intervention, balloon valvuloplasty, etc.) within 3 months prior to randomization. Participants with pacemakers are allowed in the study per investigator's discretion and after discussion with the medical monitor, and as long as it is used for prevention and there is no underlying cardiac dysfunction.
- Participant has a corrected mean QTcF > 450 msec for male participants and > 480 msec for female participants at screening or randomization. If QTcF exceeds these limits, 1 additional triplicate ECG can be repeated on the same day in order to determine the participant's eligibility.
- 14. ECG evidence of acute ischemia, atrial fibrillation or active conduction system abnormalities. The following conduction system abnormalities may be permitted per the investigator's discretion, only after discussing the case with the medical monitor:
 - a. First degree atrioventricular (AV)-block
 - b. Second degree AV-block Type 1 (Mobitz Type 1/Wenckebach type)
 - c. Right bundle branch block
 - d. Left fascicular block
 - e. Bi-fascicular block
- 15. Participant requires any ventilatory support, inclusive of any respiratory device to support breathing such as home ventilators and any form of non-invasive positive pressure ventilation (including continuous positive airway pressure [CPAP], bilevel positive airway pressure [BiPAP], and average volume-assured pressure support [AVAPS]). Participants who require oxygen therapy (even by low-flow nasal cannula [LFNC]) are not candidates for this study.
- 16. Participant has severe vision impairment that, in the opinion of the investigator, may interfere with their ability to complete all study requirements.
- 17. Participant has an intractable seizure disorder that, in the opinion of the investigator, may interfere with their ability to complete all study requirements.

- 18. Active malignancy or any other cancer from which the participant has been disease-free for < 5 years, except for curative treated localized non-melanoma skin cancer (e.g., basal cell or squamous cell carcinoma).
- 19. Participant has a solid organ transplant and/or is currently receiving treatment with therapy for immunosuppression.

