7.2.4 Electrocardiogram

- A standard 12-lead ECG will be conducted as outlined in the schedule of assessments [Table 1] using both a central ECG reading laboratory and local ECG reading. ECGs at weeks 2 and 8 will be performed at the participant's home by a qualified healthcare provider from the home healthcare vendor. In case the home healthcare visit is not feasible, the visit can be conducted at the study site.
- ECGs will be recorded in triplicate (3 separate ECGs, 5 minutes resting prior to first ECG and at least 1 minute apart per time point), prior to blood draw and transmitted electronically for central reading. The mean of the triplicate ECG from central and local read should be used for treatment decisions and AE reporting.
- If the mean triplicate QTcF is > 500 msec at any time point, one follow-up triplicate ECG may be performed on the same day. If the follow-up mean QTcF is \leq 500 msec, the participant may proceed with IP. If the follow-up mean QTcF > 500 msec is confirmed, then the participant must discontinue IP.
- An ECG will also be performed within 24 hours of any of these events: an elevation of cTnI above the ULN (see Appendix 10.9 for reference range), or when there is an elevation of cTnT above the ULN (see Appendix 10.9 for reference range) or above the participant's baseline value if it was elevated, or when a participant has any signs or symptoms reflecting cardiac involvement, inclusive of new onset shortness of breath. If the ECG is within normal limits, a repeat of the abnormal troponin value (cTnI or cTnT) should be obtained. For any of the situations above, it may be required to interrupt or discontinue further administration of IP as described in [Section 8.1 Discontinuation of Individual Participant(s) from Study Treatment]. Participants with persistent cTnI or

cTnT elevations, abnormal ECG or abnormal echocardiogram should undergo cardiology follow up.

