6.8 Additional Conventions

6.8.1 Analysis Windows

Day 1 and Day -1 are defined as the day of start taking the IP and its prior day, respectively.

The following analysis window will be used.

The data summary by visits will be done following the analysis windows specified in the table below:

Analysis Visits	Scheduled Day in	Analysis Windows (day)
	Protocol	
Screening	Day -28	-35 to -14
Week 0 (Baseline)	Day -2 to 1	-2 to 1
Week 1	Day 8	5 to 13
Week 2	Day 14	14 to 18
Week 3	Day 22	19 to 25
Week 4	Day 29	26 to 42
Week 8	Day 57	43 to 70
Week 12	Day 85	71 to 98
Week 16	Day 113	99 to 126
Week 20	Day 141	127 to 154
Week 24	Day 169	155 to 182
Week 28	Day 197	183 to 210
Week 32	Day 225	211 to 238
Week 36	Day 253	239 to 266
Week 40	Day 281	267 to 294
Week 44	Day 309	295 to 322
Week 48	Day 337	323 to 350
Week 52	Day 365	351 to 378
End of Double Blind Part	Day 365	2 to 378
Follow-up	The last dose + 28	The last dose + 28 days to the last dose +
-	days	35 days

For the analyses of safety and efficacy, for all analysis visits excluding follow-up visit, the data "by the last dose + 7 days" and the data before the first dose date of open label extension part will be included.

If more than one observation exists within the analysis window, the observation closest to the scheduled visit day will be selected for that visit. If there are two observations that have the same distance from the scheduled day, the value that is after the scheduled day will be selected in the analysis. If more than one observation is made on the same day, an average value if continuous or the worst value if categorical will be included in the analysis.

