6.5.4 Electrocardiograms

6.5.4.1 Routine 12-lead Electrocardiograms

The number and percent of participants with normal, not clinically significant abnormal, and clinically significant abnormal results as assessed by site principal investigator for the 12 lead ECG will be tabulated by analysis group and time point. Continuous 12-lead Electrocardiogram.

For all analyses, replicates at each visit will be averaged for each continuous ECG parameter.

ECG parameters [Heart Rate (bpm), PR Interval (ms), QRS Interval (ms) and QTcF (ms)] read by the central laboratory will be summarized using mean, standard deviation, minimum, maximum and median for each analysis group at each visit, including changes from baseline.

The QTcF interval will be summarized using frequency tables for each visit for values of clinical importance using the range criteria below.

	QTcF Interval Criteria Value (msec)
Normal	\leq 450
Borderline	> 450
Prolonged	> 480
Clinically significant	> 500

QTcF: QT interval using Fridericia's correction.

The QTcF interval will also be summarized by the frequencies of participants with an increase from baseline of clinical importance using the criteria identified below. These summaries will be provided for each visit.

Variable	Change from Baseline
QTcF Interval (msec)	\leq 30
	> 30
	> 60

QTcF: QT interval using Fridericia's correction.

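### QTcF outliers are counted only visit by visit, so an off-schedule QTcF above 500 msec, even a confirmed one, can be missing from every row of the QTcF tables

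*SAP*

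**What the plan says.** **QTcF tables.** Section 6.5.4.1 of both SAPs sorts QTcF into ≤ 450, > 450, > 480 and > 500 msec: "The QTcF interval will be summarized using frequency tables for each visit for values of clinical importance using the range criteria below". For increases from baseline of ≤ 30, > 30 and > 60 msec it adds "These summaries will be provided for each visit". The values are those "read by the central laboratory", and "For all analyses, replicates at each visit will be averaged for each continuous ECG parameter".

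**Choice of value.** Under section 6.8.1 of both SAPs, when a window holds several observations, "the observation closest to the scheduled visit day will be selected for that visit". A tie goes to the later one. "If more than one observation is made on the same day, an average value if continuous", that average is used. Apart from follow-up, only data up to last dose + 7 days count. The 52-week SAP also has an End of Double Blind Part row (scheduled day 365, window day 2 to 378). The 76-week SAP has an End of Treatment row (scheduled day 533, window day 2 to 560).

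**ECGs outside the schedule.** Protocol 7.2.4 applies the 500 msec limit at any time point. After a mean above it, "one follow-up triplicate ECG may be performed on the same day"; the participant must stop if the repeat is also above 500 and may proceed if it is not. Ad hoc ECGs follow a troponin rise or cardiac symptoms. Table 1 (footnote d) asks participants who stop treatment to attend end-of-treatment assessments promptly, and these include a 12-lead ECG.

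**Other safety markers.** Sections 6.5.2 and 6.5.2.1 of both SAPs count participants who meet amylase, lipase, troponin and liver thresholds at any time from first dose to 28 days after last dose (or OLE entry in the 52-week SAP).

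**The concern.** The 12-lead ECG is listed under the primary safety objective, and protocol 2.3.1.3 names heart toxicity as an important potential risk. The ECGs most likely to show a long QTcF include those taken because of a troponin rise or symptoms, and these do not fall on the scheduled day. A rule that keeps the value nearest the scheduled day tends to discard them. QTcF has a numeric stopping threshold in the protocol, yet unlike the laboratory markers it has no any-time count.

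The arms are small. One participant is 1/22 = 4.5% of a planned arm, or 1/11 = 9.1% if the 33 interim participants split evenly (an assumption). One missing case can change what the comparison with placebo shows.

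**Working it through.** The plan states no figure to reproduce. The check applies the section 6.8.1 rules to ECG series. The QTcF values and days are hypothetical, chosen to test the rules.

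**Inputs.** Week 1 window 5–13 (scheduled day 8); Week 12 window 71–98 (scheduled day 85); End of Double Blind Part window 2–378 (scheduled day 365); cut-off at last dose + 7 days.

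**Main example.** Day 85 = 470. Ad hoc ECG on day 90 = 512, repeat 508 (confirmed, last dose day 90). End-of-treatment ECG on day 93 = 475. The cut-off is 90 + 7 = day 97, so all three days are eligible.

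- Day 90 value: (512 + 508)/2 = 510.
- Week 12: distances from day 85 are 0, 5 and 8, so day 85 is taken and the row shows 470.
- End of Double Blind Part: distances from day 365 are 280, 275 and 272, so day 93 is taken and the row shows 475.
- End of Treatment in the 76-week SAP: distances from day 533 are 448, 443 and 440, so day 93 is again taken.

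No row exceeds 500.

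**Variants (52-week SAP).**

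| Series (msec) | Weekly row | End of Double Blind Part | > 500 shown? |
|---|---|---|---|
| Main example | Week 12: 470 | 475 | No |
| Visit on day 82 (inside the ± 3-day window): 512, 508; day 85: 475 | Week 12: 475 | 475 | No |
| Day 3: 512, 508; day 6: 475 | Week 1: 475 (days 2–4 are in no weekly window) | 475 | No |
| Main example with no ECG between day 91 and day 97 | Week 12: 470 | 510 | Yes |
| Stop on day 85 itself: 512, 508; day 88: 475 | Week 12: 510 | 475 | Yes |

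**How often the rules can do this.** Assume ECGs on the version 9.0 days 14, 29, 57, 85 and 169. Place a confirmed unscheduled stop on each other day from 2 to 182, which gives 181 − 5 = 176 days.

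| End-of-treatment ECG after the stop | Days on which no row exceeds 500 |
|---|---|
| 1 day | 138/176 (78%) |
| 3 days | 130/176 (74%) |
| 5 days | 122/176 (69%) |
| 7 days | 114/176 (65%) |
| None within 7 days | 0/176 |

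These are shares of possible days. They are not probabilities that a case occurs.

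**Same-day averaging.** If both triplicate means exceed 500, their average exceeds (500 + 500)/2 = 500, so averaging alone cannot hide a confirmed stop. It can hide a first reading that the repeat did not confirm: (512 + 486)/2 = 499.

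**Participants who continue.** After an unconfirmed reading, or an outlier in the > 480, > 30 or > 60 msec categories, treatment normally goes on. A later scheduled ECG then fills the end-of-period row, so a nearer ECG in the same window is enough to hide the value.

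**The case against.** **The end-of-period row catches the stopping ECG.** This is right when nothing later is recorded within last dose + 7 days, as the variants show. A reader might infer that every off-schedule stop disappears, and the documents do not support that. But the protocol asks for a prompt end-of-treatment visit with an ECG, so a later value is likely.

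**Averaging hides stops.** A reader might infer this from the same-day rule. It does not follow: the stop needs both means above 500, and two such means cannot average to 500 or less.

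**Baseline is inflated.** Exclusion criterion 13 allows one "additional triplicate ECG can be repeated on the same day in order to determine the" participant's eligibility. With 462 and then 446 at randomization, the Week 0 same-day rule gives (462 + 446)/2 = 454, so a later 478 is +24. A reader might infer a settled upward bias. But protocol 9.4.1 takes the last non-missing observation before first dose, which gives 446 and +32. The two rules compete, and the documents do not settle which applies to ECGs. Nor is the repeat clearly the better baseline, since it is accepted only because it fell within the limit.

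**The case is visible elsewhere.** Protocol 9.4.3.5.2 lists individual replicates and averages, and the disposition, withdrawal and special-interest event tables may show the participant. That stands: the value is lost from the QTcF tables, not necessarily from the report. Those outputs do not replace a count of QTcF outliers by arm.

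**Few cases are expected.** Protocol 2.3.1.1 and 2.3.1.2 report no QT prolongation in monkeys or in the first-in-human study. The cTnT-triggered ECG was never in force, because all participants were under version 7.0 or earlier (52-week SAP 5.4.3). Both points limit how often this can happen. They do not alter the rule.

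**The layout follows the protocol.** Protocol 9.4.3.5.2 also reports by time point and visit and has no worst-value row. The TLF specifications are not in the documents and might contain one, but neither SAP requires it.

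**Conclusion.** The gap holds in a conditional form. Followed as written, both SAPs can leave an off-schedule QTcF above 500 msec, including a confirmed one, out of every row of the QTcF tables. Two conditions are needed. First, another ECG in the same window lies nearer the scheduled day, or the value falls on days 2 to 4. Second, a later, lower ECG within last dose + 7 days fills the end-of-period row. Visit slotting causes this; same-day averaging hides only unconfirmed readings.

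The day counts rest on the version 9.0 ECG schedule and a single end-of-treatment ECG. Participants followed version 7.0 or earlier, whose schedule is not in the documents. The number of real cases is unknown and may be zero. The point is worth acting on because the remedy is cheap.

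**What to change.** In section 6.5.4 of both SAPs, or as a documented change in the CSR as section 1 of each SAP provides:

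- Keep the by-visit tables.
- Add participant-level any-post-baseline rows for QTcF > 450, > 480 and > 500 msec and for increases > 30 and > 60 msec. Use the maximum triplicate mean over all centrally read ECGs, scheduled and unscheduled, up to last dose + 28 days (or OLE entry in the 52-week SAP). In the 76-week SAP, count from the first ASP0367 dose.
- Do not average an initial triplicate with its repeat.
- Footnote the repeat value for each reading above 500 msec. Also footnote any value above 500 seen only on the local read, because protocol 7.2.4 uses central and local reads for treatment decisions while the tables use the central read alone.
- Separately, reconcile the ECG baseline between protocol 9.4.1 and the SAPs' Week 0 same-day averaging, and state one rule.

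The cost is some wording and one added table per SAP, with no new data and no change to any clinical rule. The small downside is that unconfirmed readings will appear and need the footnote.
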